6.7 BASELINE, TIME WINDOWS AND CALCULATED VISITS

Measurements collected at Visit 2 will be used as baseline with the exception of the activity endpoints which are averaged over 2 weeks. For endpoints of physical activity monitoring, baseline will be the average value in two weeks prior the day before first administration (Visit 2) except for Day -2 and Day -1. These will be defined as "Study baseline" which will be common baseline for both period 1 and period 2.

Planned and actual study day will be included in the analysis data sets. These will both be calculated relative to the beginning of the study and to the beginning of respective study periods in the crossover design as indicated in the following table.

Table 6.7: 1 Planned and actual study days, and time windows

Visit	Relative to period start		Relative to study start	
	Planned day	Actual day	Planned day	Actual day
2	1	1	1	1
3	43	Visit 3 date – Visit 2 date + 1	43	Visit 3 date – Visit 2 date + 1
4	43	Visit 4 date – Visit 3 date + 1	85	Visit 4 date – Visit 2 date + 1
5	3	Visit 5 date – Visit 4 date + 1	106	Visit 5 date – Visit 2 date + 1

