4.2.1.3 Additional treatments

Medications allowed to controlling acute exacerbations as medically necessary during the treatment period:

- Salbutamol inhalation aerosol from MDI for p.r.n. use
- Temporary increases in the dose or addition of oral steroids are allowed during the treatment portion of the study. PFT should not occur within 7 days of the last administered dose of an increase or addition of oral steroids. These tests may be postponed up to 14 days to meet this restriction. Subsequent visits will be scheduled according to the patient's regular schedule.
- Temporary additions of theophylline preparations are allowed during the treatment portion of the study. PFT should not occur within seven days of the last dose. These tests may be postponed up to 14 days to accommodate this restriction. Subsequent visits will be scheduled according to the patient's regular schedule.

- The use of antibiotics is not restricted and may be prescribed as medically necessary for exacerbations and / or infections. If antibiotics are prescribed for a respiratory infection prior to PFT, these tests will be postponed for at least 2 days but not more than 7 days after the last dose is given. Subsequent visits will be scheduled according to the patient's regular schedule.

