Miscellaneous	Other investigational drugs (see exclusion criterion)	NOT permitted	NOT permitted	NOT permitted	NOT permitted
	Cromolyn sodium / nedocromil sodium (if prescribed for non-asthma condition)	Permitted	Permitted	Permitted	Permitted
	Antihistamines, antileukotrienes (if prescribed for non-asthma condition)	Permitted	Permitted	Permitted	Permitted
	Methylxanthines/Theophyllines (if prescribed for non-asthma condition)	Permitted	Permitted	Permitted ¹	Permitted
	Mucolytics (not containing bronchodilators; stabilized 6 wks prior to V1)	Permitted	Permitted	Permitted	Permitted

1. Use rescue medication (salbutamol) delivered by each visit.
2. Commercial long-acting bronchodilators will be discontinued prior to Visit 2 in accordance with drug restriction for PFTs.
3. Patients on LAMA/LABA combination therapy (FDC or free dose combination) should be treated with either LAMA or LABA at Visit 0. Patients treated with LAMA or LABA monotherapy for at least 3 weeks are proceeded to Visit 1 and Visit 2.
4. SAMA is allowed to be used in patients who do not use any LAMA from Visit 0 until Visit 2.

Medication restrictions for pulmonary function testing

- At least an 8-hour washout of SABA bronchodilators.
- At least an 8-hour washout of SAMA bronchodilators prior to Visit 1 and 2 (Not allowed during treatment periods).
- At least a 48-hour washout of LABA (BID or QD) prior to Visit 1 and Visit 2 (Not allowed during treatment periods).
- At least a 48-hour washout of LAMA (BID or QD) prior to Visit 1 and Visit 2 (Not allowed during treatment periods).
- The morning dose of ICS should not be taken in the 1-hour period prior to PFTs.
- Morning doses of study medication should not be taken prior to test-day (Study medication should be taken on previous day of the visit)
- A patient visit may be re-scheduled twice due to lack of medication washout compliance.
- At least a 24-hour washout of short-acting (BID or more frequent administration) theophylline preparations.
- At least a 48-hour washout of long-acting (QD administration) theophylline preparation.

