4.2.2.2 Restrictions on diet and life style

Medication washout restrictions should be adhered to as described in [Table 4.2.2.1:1](#).

Patients must remain in the building where the PFT is performed and must return to the laboratory at least 10 minutes prior to the start of each test.

On PFT days (including the Screening Visit), patients must refrain from strenuous activity for at least 2-3 days prior to PFT and throughout the testing period. Patients should also avoid cold temperatures, environmental smoke, dust or areas with strong odours (e.g. perfumes).

Coffee, tea, chocolate, cola and other caffeine-containing beverages and foods, and ice-cold beverages should be avoided the morning of or during the PFT period. Decaffeinated beverages are acceptable.

Smoking should be discouraged for the 12 hours prior to lung function testing and throughout the study day and will not be permitted in the 30-minute period prior to PFT.

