5.1.2 Secondary Endpoints

The following secondary endpoints will be assessed:

- 6-minute walk distance (6MWD [m]) after 6 weeks of treatment
- Average number of step per day (step/day) in the 2 weeks prior to Week 6
- Average daily duration (minute) of ≥ 4 metabolic equivalents (METs) in the 2 weeks prior to Week 6
- Average daily duration (minute) of ≥ 3 METs in the 2 weeks prior to Week 6
- Average daily duration (minute) of ≥ 2 METs in the 2 weeks prior to Week 6
- Average daily active strength (METs·minute) of ≥ 3 METs in the 2 weeks prior to Week 6
- 60 minutes post-dose Slow vital capacity (SVC), after 6 weeks of treatment
- 30 minutes post-dose FEV₁, after 6 weeks of treatment
- 30 minutes post-dose FVC, after 6 weeks of treatment

These are no safety issue.

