5.2.3 Activity monitoring

A physical activity monitor (HJA-750C, OMRON) is an accelerometer that is used to measure the overall movement of a patient and provided by BI.

Patients will wear the physical activity monitor every day for 2 weeks and 3 times repeat during the trial i.e. in the 2 weeks prior to Visit 2, Visits 3 and Visit 4. The device will not be worn during bathing or water sport activities. Activities that may hamper proper functioning of the equipment are limited and not likely to happen in the population studied, but should be discussed with the investigator and eventually avoided. (e.g. high impact sports).

Muscle amount (% in BW) will be measured before activity monitor measurement at Visit 1.

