5.2.2 Secondary endpoints

Secondary endpoints of efficacy will be used as described in the CTP, Section 5.1.2 “Secondary endpoints”

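### Does the SAP need to fix the on-treatment averaging window for the five activity endpoints to the day, as it does for baseline?

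*SAP*

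**What the plan says.** The readable text speaks to the window in four places.

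- **Baseline.** SAP 6.7 sets the activity baseline: "baseline will be the average value in two weeks prior the day before first administration (Visit 2) except for Day -2 and Day -1". It is a single study baseline, "which will be common baseline for both period 1 and period 2".
- **Endpoint definition.** Protocol 5.1.2 defines five of its nine secondary endpoints over the same interval, for example "Average number of step per day (step/day) in the 2 weeks prior to Week 6". SAP 5.2.2 adds nothing: "Secondary endpoints of efficacy will be used as described in the CTP, Section 5.1.2".
- **Data collection.** Protocol 5.2.3 has the monitor worn "in the 2 weeks prior to Visit 2, Visits 3 and Visit 4". The flow chart footnote on activity monitoring agrees, and Protocol 3.1 says about two weeks before the visits.
- **Restrictions near visits.** Protocol 4.2.2.2 says that "patients must refrain from strenuous activity for at least 2-3 days prior to PFT and throughout the testing period", with no limit to particular visits. Protocol 4.2.2.1 requires "At least a 48-hour washout of LABA (BID or QD) prior to Visit 1 and Visit 2", with a matching rule for LAMA; neither washout applies before Visits 3 and 4.

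SAP Table 6.7: 1 lists planned and actual visit days, counted from period start and from study start, but no averaging window. The text under the activity headings in SAP 7.5.2 is blacked out, as are some rules for exercise data in SAP 6.6.

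**The concern.** SAP 6.7 names two days to leave out at baseline and gives no reason. If the reason is the restriction on strenuous activity, the same logic applies before Visits 3 and 4, and it would look odd to keep those days on treatment. If the reason is the 48-hour bronchodilator washout, it applies only up to Visit 2, and keeping them is right. The readable text does not say which.

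The second doubt is the anchor. The endpoint is tied to Week 6, while the wear period is tied to the visit. Visits 3 and 4 have a +3 day window, Protocol 6.1 allows rescheduling within a week, and after added oral steroids Protocol 4.2.1.3 says "These tests may be postponed up to 14 days to meet this restriction". For a late visit the two anchors select different days.

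Daily activity is half of the secondary objective. Protocol 3.2 also relies on the late window to avoid olodaterol carryover in a design without washout. An unclear window could dilute five endpoints or leave a choice open until analysis.

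**Working it through.** The documents give no effect size or SD for any activity endpoint, so there is no plan figure to reproduce here and no power statement can be made. The sample size in Protocol 7.7 concerns IC only and is unaffected.

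**Baseline days.** Visit 2 is Day 1 and there is no Day 0. Days -14 to -1 without Days -2 and -1 leave Days -14 to -3, which is 12 days. A looser reading starts at Day -15 and gives 13 days. The first fits better, because the looser reading already stops before Day -1 and would make naming that day redundant.

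**Does the baseline exclusion distort the comparison?** Baseline is one value per patient, used in both periods. For a patient with both periods observed, it cancels from the within-patient contrast. Averaging 12 days at baseline and 14 on treatment therefore does not shift the treatment estimate for such patients.

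**Restricted days.** Let k be the number of restricted days (2 or 3, from Protocol 4.2.2.2) and q the share of the usual treatment effect present on them (not given; range 0 to 1).

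Dilution of the 14-day effect = (1 − q) × k/14

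| q | k = 2 | k = 3 |
|---|---|---|
| 1 | 0% | 0% |
| 0.5 | 7.1% | 10.7% |
| 0 | 14.3% | 21.4% |

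The cost of dropping the days, if daily noise is independent, is an SE ratio of √(14/12) = 1.080 or √(14/11) = 1.128. That is an increase of 8% or 13%.

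The two choices are equally efficient when 1 − (1 − q)k/14 = √((14 − k)/14):

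- k = 2: q = 1 − (1 − 0.926) × 7 = 0.48
- k = 3: q = 1 − (1 − 0.886) × 14/3 = 0.47

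These break-even values are lower limits. Correlated days, or variation between periods within a patient, shrink the SE penalty and raise the break-even. With a 2% penalty and k = 2 it is 1 − (1 − 1/1.02) × 7 = 0.86. So neither choice is shown to be better.

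**Anchor.** With Visit 3 on Day 43, both anchors give Days 29 to 42. For a visit d days late, the visit-anchored window shares 14 − d days with Days 29 to 42:

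| Visit day | Delay | Visit-anchored window | Days shared |
|---|---|---|---|
| 43 | 0 | 29 to 42 | 14 |
| 46 | 3 | 32 to 45 | 11 |
| 50 | 7 | 36 to 49 | 7 |
| 57 | 14 | 43 to 56 | 0 |

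The last row needs the whole visit and the wear period to move by 14 days. Protocol 4.2.1.3 postpones the lung function tests; it does not say that activity monitoring moves with them.

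**Which anchor would an analyst use?** Protocol 6.1 places Visits 3 and 4 after six weeks of treatment, so Week 6 serves as the label of the end-of-period visit. Wear is tied to the visit in every description, and the reminder calls in Protocol 6.2.2 are timed from the next planned visit. Anchoring on the visit is the natural reading, and it uses the days on which the monitor was meant to be worn.

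**The case for a change.** The strongest case for a change comes from period 2. Suppose Visit 3 slips to Day 57. Period 2 medication starts the next day, Day 58. A window fixed from study start at Days 71 to 84 would then cover treatment days 14 to 27 of period 2 (71 − 58 + 1 = 14; 84 − 58 + 1 = 27). That is not the end of the period, and it weakens the carryover argument in Protocol 3.2. The longest delays also follow exacerbation treatment, so the anchor could decide whether those days are averaged. And SAP 6.7 is the natural home for such a rule.

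Some of this stands: the readable text gives no rule for late visits. But the damaging version needs an anchor that ignores the visit and the period start. SAP Table 6.7: 1 already counts days from the start of each period, and Protocol 6.1 asks that rescheduled visits preserve at least six weeks of treatment. A window ending at the actual visit does not have this problem. The choice cannot be steered by treatment either, because Protocol 4.1.5.1 and 7.6 keep analysts blinded until database lock.

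On the restricted days, the missing reason for the baseline exclusion is a real omission. It does not create doubt about the on-treatment rule, because the SAP names excluded days where it wants them and names none after baseline. The restriction covers strenuous activity only, in patients who walk less than 400 m in six minutes with a Borg score of at least 4. Steps and time at 2 METs or more should be little affected; time at higher METs could be affected somewhat more.

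**Conclusion.** No change is called for. On a plain reading the on-treatment value is the average of all days in the two weeks before the end-of-period visit. The exclusion of Day -2 and Day -1 is not shown to be an error, and the bronchodilator washout before Visit 2 is a plausible reason for it.

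What remains is a missing detail about late visits, which analysts can settle sensibly under blinding. It touches only patients whose visit is late, and the documents do not say how many to expect. The restriction and the window rule are the same for both treatments, so they favour neither. Any dilution from the restricted days lies between 0% and 21%, depending on an effect share that the documents do not give, and dropping the days would cost precision in return. The primary endpoint and its sample size are untouched.

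This rests on two assumptions: that one rule is used in both periods, and that the blacked-out SAP text does not contradict the plain reading. That text covers the same five endpoints and may already give the window, so the plan cannot be said to lack one.

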7. PLANNED ANALYSIS

For End-Of-Text tables, the set of summary statistics is: N / Mean / Standard deviation (SD) / Min / Median / Max.

Tabulations of frequencies for categorical data will include all possible categories and will display the number of observations in a category as well as the percentage (%) relative to the respective treatment group (unless otherwise specified, all patients in the respective patient set whether they have non-missing values or not). Percentages will be rounded to one decimal place. The category missing will be displayed only if there are actually missing values.

7.1 DEMOGRAPHIC AND OTHER BASELINE CHARACTERISTICS

Only descriptive statistics for the treated set are planned for this section of the report.

7.2 CONCOMITANT DISEASES AND MEDICATION

Only descriptive statistics are planned for this section of the report.

Use of pulmonary medications during treatment period and testing will be summarised in the end-of-text tables in the Clinical Trial Report (CTR) and a subject data listing of all concomitant medications will be provided in Appendix 16.2.

A table of number (%) of patients with concomitant diagnoses by system organ class (SOC) and preferred term (PT) will be included along with a supporting subject data listing. Concomitant diagnoses will be coded with the most recent version of the Medical Dictionary for Regulatory Activities (MedDRA) in effect at database lock.

Descriptive statistics and frequency tables (%) will be presented for history of trial indication.

Frequency tables (%) will be presented for COPD background characteristics.

7.3 TREATMENT COMPLIANCE

Only descriptive statistics are planned for this section of the report. Summary statistics will be given for percent compliance along with the number (%) of patients with compliance in the categories <80%, 80% - 100% (cf. [Section 5.4](#) for calculation of treatment compliance).

7.4 PRIMARY ENDPOINT

The primary analysis for Inspiratory capacity (IC) will be conducted using mixed effect repeated measurement including treatment and period as categorical fixed effects, study baseline as a covariate and patient as a random effect treatment. Compound symmetry will be used as a covariance structure for within patient variation. The SAS procedure MIXED will be used involving the restricted maximum likelihood estimation and the Kenward-Roger approximation for denominator degrees of freedom. This approach is described in [\(2\)](#). Adjusted mean values as well as treatment contrasts will be presented together with the 95% confidence intervals and p-values.

If the number of patients in PPS is less than 90% of the number of patients in FAS, the primary analyses will also be performed on PPS. These will be supportive analyses to assess the robustness of the primary analysis using FAS.

Descriptive statistics by treatment will be displayed.

7.5 SECONDARY ENDPOINTS

7.5.1 Key secondary endpoint

This section is not applicable as no key secondary endpoint has been specified in the protocol.

7.5.2 Secondary endpoints

The analysis will be performed as defined in the CTP, Section 7.3.2.

Descriptive statistics by treatment will be displayed.

Additional analysis are described follows.

7.5.2.1 Average number of step per day (step/day) in the 2 weeks prior to Week 6

[REDACTED]

7.5.2.2 Average daily duration (minute) of ≥ 4 metabolic equivalents (METs) in the 2 weeks prior to Week 6

[REDACTED]

7.5.2.3 Average daily duration (minute) of ≥ 3 METs in the 2 weeks prior to Week 6

[REDACTED]

7.5.2.4 Average daily duration (minute) of ≥ 2 METs in the 2 weeks prior to Week 6

[REDACTED]

7.5.2.5 Average daily active strength (METs·minute) of ≥ 3 METs in the 2 weeks prior to Week 6

[REDACTED]

[REDACTED]

7.7 EXTENT OF EXPOSURE

Extent of exposure is calculated as drug stop date minus drug start date plus one day and treatment interruptions are not taken into account in the calculation.

Extent of exposure will be summarised using descriptive statistics for the total treatment exposure in days as well as tabulation of number of patients with total exposure fall into the following categories:

- 1 day
- 2 – 21 days
- 22 – 42 days
- 43 – 63 days
- 64 - 84 days
- ≥ 85 days.

7.8 SAFETY ANALYSIS

All safety analyses will be performed on the treated set.

7.8.1 Adverse events

The analyses of AEs will be descriptive in nature and will be based on BI guideline 'Handling and summarisation of AE data for CTRs and integrated summaries' (3). All analyses of AE will be based on the number of patients with AEs and NOT on the number of AEs. For this purpose, AE data will be combined in a 2-step procedure into AE records.

In the first step, AE occurrences, i.e. AE entries collected in the eCRF, will be collapsed into AE episodes provided that all of the following applies:

- The same MedDRA lowest level term was reported for the occurrences
- The occurrences are time-overlapping or time-adjacent (time-adjacency of 2 occurrences is given if the second occurrence started on the same day or on the day after the end of the first occurrence)
- Treatment did not change between the onset of the occurrences OR treatment changed between the onset of the occurrences, but no deterioration was observed for the later occurrence.

In the second step, AE episodes will be condensed into AE records provided that the episodes were reported with the same term on the respective MedDRA level and that the episodes are assigned to the same treatment. For further details on summarisation of AE data, please refer

to BI guideline 'Handling and summarisation of AE data for CTRs and integrated summaries' (3).

Analyses of AEs are based on the concept of treatment emergent adverse events. This means that all AEs occurring between first drug intake and 21 days after last drug intake are assigned to the respective analysing treatment. All AEs occurring before first drug intake are assigned to 'screening' and all AEs occurring after last drug intake + 21 days up to and including trial completion date are assigned to 'post-treatment'. AEs more than 21 days after drug stop date for a period but before the start of the next period will be assigned to 'washout'. AEs starting after trial completion date are assigned to 'post-study'. Screening, post-treatment and post-study AEs are presented in subject data listings only. For details on the treatment definition, see [Section 6.1](#).

An overall summary of AEs will be presented.

The frequency of patients with AEs will be summarised by treatment, primary SOC and PT. Separate tables will be provided for patients with other significant adverse s according to ICH E3 (4), for patients with AEs leading to treatment discontinuation, for patients with AEs leading to death, for patients with investigator determined drug-related adverse events, and for patients with SAEs.

According to ICH E3 (4), AEs classified as 'other significant' include those non-serious and non-significant adverse events with

- (i) 'action taken = discontinuation' or 'action taken = reduced', or
- (ii) marked haematological and other lab abnormalities or that lead to significant concomitant therapy as identified by the Clinical Monitor/Investigator and confirmed at a BRPM.

The system organ classes will be sorted according to the standard sort order specified by the European Medicines Agency, PTs will be sorted by frequency (within SOC).

Standard AE analyses requested for public disclosure at CT.gov and European Union Drug Regulating Authorities Clinical Trials will also be provided in Section 16.1.9.2 of the CTR.

7.8.2 Laboratory data

Clinically significant findings in laboratory data will be reported as "baseline conditions" or "adverse events" and will be analysed accordingly.

